### **7.2.3. Dose Modification**

There will be no dose adjustment in this study.

### **7.3. Blind and Unblinding**

This study is a single-arm trial, blind method and unblinding are not applicable.

### **7.4. Treatment Compliance**

Study drug will be dispensed by the responsible study personnel. Drug accountability and compliance check results should be documented in the participant's study records.

Participants should be instructed on the importance of taking the study drug as directed when a migraine attack occurs (mild, moderate, or severe). At site visits, the responsible study personnel will review the use of study drug recorded in the BYOD and the returned study drug to assess treatment compliance. Dose discrepancies reported by BYOD, review of study drug, and information provided by the participant must be documented in the original medical record. Data in BYOD for incorrect or missing doses and migraine headaches will be corrected by the Data Clarification Record or Study Drug Reconciliation Form. The investigator shall inform the participants participating in the study that if it is confirmed that the participants are lack of compliance, the participants will be terminated to continue to participate in the study. During monthly study visits, if a participant's BYOD records a lack of compliance, the study staff should contact the participant and document this contact in the original medical record to identify potential participant loss to follow-up as early as possible.

Investigators should monitor participants for possible abuse of the study drug (participants taking the study drug for non-therapeutic purposes, such as for elevated or excited mental effects). The investigator should also assess study drug accountability discrepancies (e.g., missed study drug, lost study drug, overuse of study drug). In the event of a study drug accountability discrepancy, the investigator should obtain additional information and explanation from the participant.

Potential cases of study drug abuse or overdose (including failure to return study drug for participants who fail to take the study drug as instructed or discontinue treatment) should be recorded in original medical records, and AEs or SAEs should be reported as appropriate. Protocol deviations should be documented in the event of dose errors (e.g., taking more than 1 tablet on a calendar day).

### **7.5. Investigational Product Management**

The sponsor/its authorized personnel are responsible for providing the investigational product to the investigator and the site. The sponsor/its authorized personnel shall not provide the investigational drugs to the investigators and clinical trial institutions before the clinical trial is approved by the ethics committee and approved or filed by drug regulatory authorities.

The sponsor / its authorized personnel should provide the investigator and institution with a written description of the investigational product, specifying the use, storage, and records of the investigational product. The sponsor/ its authorized personnel will establish procedures for investigational product administration and management, including receipt, storage, dispensing, use, and return. Investigational products returned from participants and unused by study personnel should be returned to the sponsor or destroyed by the study site upon authorization by the sponsor.

The sponsor / its authorized person should ensure that the investigational product is delivered to the investigator and institution in a timely manner to ensure that it is used by the participants; keep the records of transportation, receipt, distribution, recovery and destruction of the investigational product; establish the investigational product recovery management system to ensure the recall of defective products, recovery after the trial is completed and recovery after expiration. All unused and/or partially used study drug can be sent to the predetermined drug destruction facility only after being inspected and reconciled by the responsible Study monitor or the sponsor's designee. If it is site policy to destroy study drug on site, it is the Investigator's responsibility to ensure that arrangements have been made for the disposal, procedures for proper disposal have been established according to the applicable regulations, guidelines and institutional procedures, and appropriate records of the disposal have been documented. Destruction at a study site may only occur after being inspected and reconciled by the responsible Study monitor or the sponsor's designee.

The management of investigational product in the study site is in the charge of the investigator's authorized study staff; the investigational product could only be prescribed by the principal investigator or the study doctor authorized by the principal investigator, and it was necessary to ensure that all investigational products are only used for the participants in the clinical trial and their dosage and administration should follow the study protocol; if there is a problem in the quality or appearance of the investigational product, the sponsor should be contacted immediately; the unused remaining investigational product and empty packages of the used investigational product will be returned by the investigator's authorized study staff.

The investigator should designate a person to be responsible for the receipt, storage, dispensing, use, recovery, inventory, and recording of the investigational product, and the records should ensure that the contents are completed in a timely and accurate manner; the drug receipt form must be signed in duplicate, with the study site and the sponsor holding one copy.

The Clinical Research Associate is responsible for monitoring the receipt, storage, use, inventory, and recovery of the remaining investigational product and empty packages of used product. After drug accountability at the visit, medication errors, overdose, and drug loss should be recorded in the original medical records and eCRF. After checking by the Clinical Research Associate, the remaining investigational products and empty packages of used drugs will be returned by the sponsor (both parties will sign the drug recovery form). At the end of the trial, investigational product shipment records must be consistent with used and destroyed/returned quantities. Any discrepancies will be documented and the reason for the discrepancy noted.

The sponsor / its authorized person should take measures to ensure the stability of the investigational product during the trial. The retention period of the samples of investigational drug shall be preserved until the end of clinical trial data analysis or the time limit required by relevant laws and regulations within the storage period of investigational drug, and the longer time limit shall be taken if the two are inconsistent.

## **8. ADVERSE EVENTS**

During this study, the investigators (or authorized qualified person) should detect and record all adverse events/serious adverse events and pregnancy events observed according to the criteria and definitions in this study protocol. Investigators will evaluate adverse events, monitor the safety status of participants and provide corresponding protective measures to ensure the safety of participants, and report according to relevant requirements.

### **8.1. Definition of Adverse Events**

According to the definition in GCP, an adverse event is any untoward medical occurrence in a clinical trial participant administered an investigational product that may present with symptoms/signs, disease, or laboratory abnormalities and which do not necessarily have a causal relationship with the investigational product.

In order to collect more sufficient information, following the participant's written consent to participate in the study, information on clinical adverse events will be collected in this study. Any clinical adverse event that occurs after signing the informed consent form and before the first use of the investigational product and meets one of the following conditions should be recorded as a pretreatment adverse event: injury/damage caused by any clinical laboratory test procedure; adverse event caused by drug discontinuation related to the trial protocol; adverse event caused by drugs other than the study product (or investigational product) taken as part of the treatment regimen. TEAEs are events that start after the first dose of trial drug and do not occur or worsen relative to the first dose.

Examples of an AE include:

1. Any abnormal laboratory test results (hematology, clinical chemistry, or urinalysis) or other safety assessments (e.g., ECGs, radiological scans, vital signs measurements), including those that worsen from baseline, and felt to be clinically significant in the medical and scientific judgement of the investigator.
2. Exacerbation of a chronic or intermittent pre-existing condition including either increase in frequency and/or intensity of the condition.
3. New conditions detected or diagnosed after study treatment administration even though it may have been present prior to the start of the study.
4. Signs, symptoms, or the clinical sequelae of a suspected drug-drug interaction.

Examples of NOT meeting definition of an AE include:

1. Any clinically significant abnormal laboratory findings or other abnormal safety assessments which are associated with the underlying disease. However, it was considered an AE if the investigator considered the intensity to be more severe than the expectation for the participant 's status.
2. The disease/disorder being studied or expected progression, signs, or symptoms of the disease/disorder being studied. However, it should be considered an AE when its severity exceeds the expected severity of the participant 's condition.
3. Medical or surgical procedures (e.g., endoscopy, appendectomy). Note that the condition leading to this procedure was an AE.
4. No adverse medical condition, but hospitalization for social reasons and/or convenience.
5. Daily fluctuations within the expected range without significant deterioration in the underlying disease or condition that were present or detected at the start of the study.
6. Pre-existing conditions or signs and/or symptoms unrelated to the study intervention before the first study drug administration; These events will be documented in the medical history section of the eCRF.

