### **8.5. Time Periods for Collection of Adverse Events and/or Serious Adverse Events**

Adverse events, including serious adverse events, will be collected in this study from the time the participant signs the informed consent form until the end of the safety follow-up period. Investigators were not required to actively collect AEs or SAEs following the participant's safety follow-up period. However, if the investigator learns of any SAE, including death, at any time after a participant leaves the study, and considers the event to be reasonably related to the study intervention or study participation, the investigator must promptly collect and report.

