### **10.5.2. Safety Analysis**

The primary endpoints of this study are adverse events, common adverse events (incidence  $\geq 5\%$ ), serious adverse events, adverse events leading to study drug discontinuation, etc.; ECG, vital signs/physical measurements and clinical laboratory test abnormalities.

Adverse events will be coded using the Medical Dictionary for Regulatory Activities (MedDRA). Analysis of adverse events will be mainly based on TEAEs. All TEAEs, common TEAEs (incidence  $\geq 5\%$ ), SAEs, and TEAEs leading to study drug discontinuation will be summarized and analyzed by SOC and PT, and the AEs will be listed by participant.

Vital signs/physical measurements, ECG parameters, and laboratory tests and their changes from baseline will be summarized by visit using descriptive statistics. The number and percentage of participants with abnormal ECG, vital signs, and laboratory test (according to CTCAE grade) will be presented. LFT elevations will also be summarized with number and percentage of participants in pre-specified categories. In addition, these safety data will also be listed by participant.

Additional details can be found in the SAP.

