7.2.4 Analysis Periods

To facilitate the analyses based on eDiary data (including eDiary compliance and migraine days), the analyses for safety endpoints, the following analysis periods will be defined.

Table 1. Analysis Periods

Analysis periods	Start date/time	End date/time	Usage
OP	Screening Visit date	LT _T start date – 1 day	To be used to calculate the eDiary compliance, number of migraine days per 4 weeks in this period.
LT _T	Earlier of (1) Baseline Visit date, and (2) study drug start date	Later of (1) Week 52/EOT date, and (2) study drug last dose date	To be used to calculate the eDiary compliance and number of migraine days per 4 weeks or the overall period in the long-term treatment.
Pre-treatment safety		Study drug start date – 1 day for AEs; study drug start date/time otherwise	To be used to assess the safety endpoints prior to study drug treatment.
Treatment safety	Study drug start date for AEs; after study drug start date/time otherwise	[Later of (1) Week 52/EOT date, and (2) study drug last dose date] + 7 days	To be used to assess the safety endpoints of the treatment period.
Follow-up safety	[Later of (1) Week 52/EOT date, and (2) study drug last dose date] + 8 days		To be used to assess the safety endpoints of the follow-up period.

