7.5.2 Adverse Events

The AEs will be coded by the latest version of MedDRA. The toxicity of AEs will be graded using National Cancer Institute Common Terminology for Adverse Events (NCI CTCAE) v5.0.

All AEs will be categorized according to the safety analysis periods (refer to Section 7.2.4), ie. pre-treatment safety period, treatment safety period, and follow-up safety period:

- Pre-treatment AEs, ie, those with imputed AE onset dates falling within the pre-treatment safety period.
- Treatment-emergent adverse event (TEAEs), ie, those with imputed AE onset dates falling within the treatment safety period. See Section 7.2.1 for AE onset date imputation.
- Follow-up AEs, i.e., those with imputed AE onset dates falling within the follow-up safety period.

Drug-related AEs are the AEs assessed by the site investigator as having a relationship to the investigational product of "definitely related", "probably related", or "possibly related".

An overall summary of AEs will display the number and percentage of participants reporting the following AEs for participants in different categories of average rimegepant exposure (< 2 , ≥ 2 to < 8 , ≥ 8 to < 14 , < 14 and ≥ 14 tablets per month) and overall participants for treatment safety and follow-up safety analysis periods, respectively, as below:

- For treatment safety analysis period, the following will be summarized using SS:
 - Any TEAE, any drug-related TEAE,
 - Any serious TEAE, any drug-related serious TEAE,
 - Any TEAE with CTCAE grade ≥ 3 , any drug-related TEAE with CTCAE grade ≥ 3 ,
 - Any TEAE leading to drug interruption; any drug-related TEAE leading to drug interruption,
 - Any TEAE leading to treatment discontinuation, any drug-related TEAE leading to treatment discontinuation,
 - Any TEAE leading to study discontinuation, any drug-related TEAE leading to study discontinuation,
 - Any TEAE leading to death, any drug-related TEAE leading to death.

- For follow-up safety analysis period, the following will be summarized using FUSS:
 - Any AE,
 - Any SAE,
 - Any AE leading to death.

Further, the number and percentage of participants with the following AEs will be tabulated by SOC and PT for participants in different categories of average rimegepant exposure (< 2 , ≥ 2 to < 8 , ≥ 8 to < 14 , < 14 and ≥ 14 tablets per month) and overall participants for treatment safety and follow-up safety analysis periods, respectively, as below:

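### The protocol's TEAE sentence contradicts itself and the SAP uses onset date only, so a pre-treatment AE that worsens under its original record is left out of the TEAE tables

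*Protocol*

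**What the plan says.** **Protocol.** Section 8.1 defines the term as "TEAEs are events that start after the first dose of trial drug and do not occur or worsen relative to the first dose". The same section lists, as examples of an AE, test abnormalities that have worsened since baseline and exacerbation of a pre-existing condition. For the time between consent and first use of study drug, 8.1 says that an event which "meets one of the following conditions should be recorded as a pretreatment adverse event". The three conditions are injury from a test procedure, an event caused by stopping a drug because of the protocol, and an event caused by another drug of the regimen. Section 8.5 is wider: AEs are collected "from the time the participant signs the informed consent form until the end of the safety follow-up period". Section 8.7 lists one start date, one end date and a severity grade for each AE. Section 10.5.2 states: "Analysis of adverse events will be mainly based on TEAEs".

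**SAP.** Section 7.5.2 sorts every AE by date. Pre-treatment AEs are "those with imputed AE onset dates falling within the pre-treatment safety period" and TEAEs are "those with imputed AE onset dates falling within the treatment safety period". Table 1 in 7.2.4 starts the treatment safety period at "Study drug start date for AEs; after study drug start date/time otherwise". There is no clause on worsening. The AE tables specified in 7.5.2 cover the treatment and follow-up periods only.

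**The concern.** AEs are the leading part of the primary endpoint, and nearly every on-treatment AE table depends on the TEAE flag. The protocol's definition of that flag cannot be followed as written. The evident intention is to count events that are new or worse after first dose, because 8.1 itself treats worsening as an AE. The SAP does not restore that intention, since an event with a known pre-dose onset stays pre-treatment whatever its later course.

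The pre-dose interval is not trivial. It covers the 30-day Observation Period, the wait for baseline laboratory review and the eligibility call, and then the time to the first treated migraine. If sites handle a grade increase differently, one extending the old record and another opening a new one, the same clinical course is counted at one site and not at the other.

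**Working it through.** **Step 1. Follow a worsening event through the rules.** The inputs are Protocol 8.1, 8.5 and 8.7 and SAP 7.2.1, 7.2.4, 7.5.2 and 7.5.3.

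| Course | How it reaches the data | SAP class | In the TEAE tables? |
|---|---|---|---|
| A. Recorded pre-dose AE, ongoing, grade rises after first dose | Original record continued | Pre-treatment | No; listings only |
| B. Same course | New AE record dated at the worsening | TEAE | Yes |
| C. Pre-dose condition held in medical history, then exacerbated | New AE under 8.1 | TEAE | Yes |
| D. Pre-dose event not recorded because it is outside the three conditions in 8.1, then worse | New AE, if entered with the date of worsening | TEAE | Yes |
| E. AE with a wholly missing start date and no end date before first dose | Start imputed to first dose date | TEAE | Yes |
| F. Laboratory value that worsens from baseline | CTCAE and LFT shift tables | Does not use the flag | Shown separately |

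Only course A is lost. It needs three things together: a pre-dose event entered as an AE, still ongoing at first dose, and worsening kept under the same record. Neither document says whether a grade increase opens a new record, so the choice between A and B is left open. Protocol 8.5 makes the pool for A larger and the three conditions in 8.1 make it smaller. Even the narrow pool need not be empty, because Protocol 5.4 and 5.5 require some drugs to be stopped at or before the Baseline Visit, which falls before first dose.

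**Step 2. Reproduce the plan's own AE figures.** With N = 240 (Protocol 10.2, SAP 3.4), P(at least one) = 1 − (1 − p)^240.
- p = 5%: 1 − 0.95^240 = 99.9995%; the plan says >99.9%.
- p = 1%: 1 − 0.99^240 = 91.04%; the plan says 91.0%.

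Both agree, and the point does not dispute them.

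**Step 3. Look for a size.** No document gives the number of pre-treatment AEs, the share ongoing at first dose, or the share that worsen. As pure illustration, assume that a fraction f of participants with a given event are lost through course A, so that p becomes p(1 − f):

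| f (assumed) | P(at least one), true rate 1% | P(at least one), true rate 5% |
|---|---|---|
| 0 | 91.0% | >99.9% |
| 10% | 88.6% | >99.9% |
| 20% | 85.5% | >99.9% |
| 50% | 70.0% | 99.8% |

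These rows show sensitivity and are not estimates. One participant can also matter at the cut-off for a common TEAE: 12/240 = 5.0% qualifies, while 11/240 = 4.6% does not.

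**The case against.** The strongest reply is that the protocol sentence is an editorial slip with no effect on programming, because the SAP's date rule is clear. Most worsening is also caught elsewhere, as courses B to F show. The two protocol provisions even pull against each other: if 8.1 keeps most pre-dose events off the AE form, those events have no pre-dose onset date and cannot be misclassified. The CRF and the eCRF Completion Guidelines, which are cited but are not part of the protocol or SAP, may already tell sites to open a new record when the grade rises.

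Much of this stands, and it limits the size of the problem. It does not remove course A, which follows from a stated rule and not merely from a missing detail. The reply is also right that a worsening clause in the SAP achieves nothing if the database holds one grade per event and no new record is opened. The recording rule is therefore the part of the correction that makes the clause work.

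A reader might infer two stronger points that the documents do not support.
- *That such events vanish from the primary endpoint.* They leave the TEAE tables, not the database. All AEs are listed with their period flag, and the laboratory, vital-sign and ECG abnormality analyses do not use AE onset dates.
- *That TEAEs of grade 3 or higher are especially understated.* Nothing in the documents shows that the loss is concentrated there. The separate listings of AEs of grade 3 or higher, and of AEs leading to discontinuation, interruption or death, are specified for all AEs and not only for TEAEs.

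**Conclusion.** The point holds in this limited form. The 8.1 sentence contradicts itself. Under the SAP's onset-only rule, a recorded pre-treatment AE that is ongoing at first dose and worsens under its original record is left out of the TEAE incidence, grade, serious, drug-related and discontinuation tables. Such events can be lost; the documents do not show that any will be.

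The size cannot be derived and is probably small. A reader might be tempted to supply it, for instance by assuming that 10–20% of 240 have an ongoing AE at first dose and that 5–10% of those worsen: 240 × 0.10 × 0.05 = 1.2 to 240 × 0.20 × 0.10 = 4.8 participants. That should not be relied on. Neither share is in the documents, and the upper one sits badly with the three-condition limit in 8.1. The result pools all event types, so it is not comparable with the 1% and 5% rates in Protocol 10.2 if those are read as rates of a single event. In the any-TEAE row, a participant is missed only if they have no other TEAE.

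The conclusion assumes that no unseen CRF instruction already forces a new record on worsening. It changes no sample-size figure. It should be corrected because the flag governs the main AE tables of a safety study and the correction is cheap.

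**What to change.** 1. Reword the TEAE sentence in Protocol 8.1 to: *events that start on or after the first dose, or were present before it and worsened after it*. This also removes a small mismatch, since the protocol now counts from after the first dose and the SAP from the study drug start date.
2. Put the same clause in the SAP 7.5.2 TEAE rule: *or a pre-treatment AE whose CTCAE grade increases on or after the study drug start date within the treatment safety period*.
3. State that a grade increase in an ongoing pre-treatment AE, on or after the study drug start date, is entered as a new AE record with the date of worsening as its onset. Otherwise, state how the worsening is derived from the data held. If the new-record route is used, the SAP's date rule then counts these events without further programming.
4. Reconcile Protocol 8.1 (three conditions) with 8.5 (all AEs from consent) on which pre-dose events are recorded as AEs and which go to medical history.

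The cost is wording in both documents, one recording or derivation rule and at most one programming condition. For data already collected, ongoing pre-treatment AEs would need a check for later grade increases before the flag is final.
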